### **2.3.2 Known Potential Benefits**

There is no guarantee of benefit to subjects who will enroll in this protocol. However, seasonal influenza vaccine is considered beneficial to most subjects, as it generally provides protective immunity against the influenza strains within the vaccine. If vaccine is administered after flu season, there is no benefit to the subject. Data from this study may yield a better understanding of the current body of knowledge describing human infections with influenza viruses.

### 3 OBJECTIVES AND OUTCOME MEASURES

#### 3.1 Study Objectives

Primary Objectives:

To characterize HA-specific plasmablasts and memory B cells after influenza vaccination

Secondary Objective:

To investigate the longevity of humoral immunity to influenza virus in humans

#### 3.2 Outcome Measures

##### 3.2.1 Primary Outcome Measures

- Determine the percentage of subjects achieving seroconversion, defined as the percentage of subjects with either a pre-vaccination HI titer < 1:10 and a post-vaccination HI titer > 1:40 or a pre-vaccination HI titer > 1:10 and a minimum four-fold rise in post-vaccination HI antibody titer (day 0, 28).

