## 2 BACKGROUND INFORMATION AND SCIENTIFIC RATIONALE

### 2.1 Background Information

Annual influenza virus epidemics by subtype A viruses (H1N1 and H3N2), and/or influenza B viruses have been shown to cause substantial morbidity and mortality, exacting an average of 36,000 deaths and more than 200,000 hospitalizations in the US alone (1).

To combat this important public health threat, two types of inactivated influenza vaccines have been approved by the FDA: 1) a trivalent, inactivated vaccine (TIV); and 2) a quadrivalent inactivated vaccine (QIV). The TIV vaccine contains the hemagglutinin (HA) and neuraminidase (NA) proteins corresponding to the three influenza viruses predicted to be in circulation during the influenza season (two A strains and one B), and the quadrivalent type contains the HA and NA for an additional B strain. These vaccines induce predominantly HA-specific and NA-specific antibodies that are capable of virus neutralization. Antibodies to HA are critical to provide immune protection to the host against influenza virus infection, as this protein plays a key role in virus entry to initiate the replication cycle in the cell. A live attenuated vaccine has also been approved but this study will use only inactivated influenza vaccine.

Currently, the Advisory Committee on Immunization Practices of the CDC recommends that everyone aged 6 months or older in the United States receive the influenza vaccine on an annual basis (2). The recommendation for annual vaccination, regardless of previous vaccination history, is in part due to the constantly changing nature of the influenza strains in circulation. Through the processes of antigenic drift and antigenic shift, the viral HA protein is constantly changing to evade the antibody response. This requires that the formulation of the influenza vaccine must be updated each season. However, when the vaccine formulation remains unchanged from year to year, re-vaccination is still recommended because antibody levels decline over the course of a year (3).

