#### 4 STUDY DESIGN

Longitudinal assessment of the study participants will be made at every study visit. Assessments will be performed at day 0, 7, 14, 28, 90 and 180 days after immunization as outlined in the Schedule of Events (appendix A). Participants will be monitored by the study nurse for the presence of both expected reactions to vaccination and for unexpected adverse reactions for 15 minutes following vaccination. Subject enrollment will be contingent upon the availability of the seasonal flu vaccine and will end upon expiration of the product.

Due to the COVID-19 pandemic, all non-essential research was halted in mid-March 2020. New enrollments were placed on hold for this study. Follow-up visits were also halted, which impacted the timing of participants' subsequent follow-up visits. For this study, there are participants whose Day 180 visits were impacted. We will request an expansion of the study window for the participants whose Day 180 visits were impacted. Additional details regarding this are detailed further in the protocol. None of the other visits were impacted.

The clinical study is designed to characterize the specific immunologic response to influenza vaccination of humans using commercially available influenza vaccine. This study will compare and contrast the response of individual components of the immune system using licensed seasonal inactivated influenza vaccine. This vaccine is FDA approved for protection against influenza infection but may have different effects on different components of the immune system. The enrollment goal is up to a total of 70 subjects. The subjects will have blood drawn at designated time points to have ex-vivo analysis of specific immunologic responses measured. Blood will be drawn at screening, day 0, 7, 14, 28, 90 and 180 study visits.

Due to the COVID-19 pandemic, there are participants whose Day 180 visits were impacted. We are requesting that the window for the day Day 180 visit be expanded by 90 days. Day 180 is the final visit/study endpoint for this study.

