## 5 STUDY POPULATION

The study will enroll 10 healthy volunteers per vaccination season in years 1, 2, and 4, to analyze the immune response to influenza vaccination in healthy individuals. For years 5 and 6, we anticipate enrolling a maximum of 20 participants, to analyze the immune response to influenza vaccination in healthy individuals.

Total enrollment goal is up to a total of 70 subjects. Individuals who complete the study will be given the option to re-enroll in subsequent years as long as they continue to meet all inclusion/exclusion criteria. Re-enrolling subjects will be re-consented, given new subject identifiers, and counted towards the enrollment number goal for each year of participation.

- Males and non-pregnant females confirmed to be non-pregnant immediately prior to vaccination, aged 18 - 49, inclusive.
- Study subjects will be drawn from existing populations of students, staff, faculty, or volunteers at Emory University or other eligible healthy adults who may hear of the study by word of mouth.
- Study subjects will be recruited via word of mouth and placement of recruitment flyers in key locations on campus. Social media messaging via Facebook and Twitter will also be used in an effort to increase the number of enrollees into this study.

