#### Research Laboratory Assays:

- Innate responses in the blood and mucosal sites: The serum analyses of cytokines and chemokines associated with innate immunity will be determined by multiplex analysis,, including IP-10, Th1 cytokines (IFN- $\gamma$ , TNF, IL-2), Th2 (IL-4, IL-5, IL-13) and regulatory (IL-10) cytokines. Flow cytometric analysis of innate cell populations (dendritic cell subsets, monocyte subsets, NK cell subsets and innate lymphoid cells) will be performed using antibody panels routinely in use in the research laboratory
- B cell and CD4 T cell responses: The following influenza virus-specific responses will be analyzed in the blood after vaccination:
  - Serum antibody: We will measure the HAI titers, neutralizing antibody responses, and the influenza-specific serum antibody levels (IgG, IgA, and IgM) using ELISA at all time-points.
  - Plasmablasts: The influenza-specific plasmablast response will be quantitated using both ELISPOT and flow cytometry at day 7 post-vaccination.
  - Memory B cells: The kinetics of the IgG memory B cell influenza-specific response will be quantitated using an established assay.
  - CD4 T cells: The HA-specific CD4 T cell responses will be quantitated at each time point by ex vivo stimulation using overlapping HA peptides or HA protein of the different influenza strains present in the vaccine. The following cytokines will be analyzed using ICS or ELISPOT: Th1 cytokines (IFNg, TNF- $\alpha$ , and IL-2); Th2 cytokines (IL-4 and IL-10); and TFH cytokines (IL-21 and IL-4). We will put a specific focus on analyzing CD4 T follicular helper (TFH) responses since these cells specialize in B cell help and are critical for the formation and maintenance of germinal centers. The germinal center reaction, in turn, is necessary for the generation of high affinity antibody responses and memory B cells. In addition, TFH cells secrete the cytokine IL-21 that is essential for generating long-lived plasma cells and sustaining antibody responses. Therefore the generation of long-term humoral immunity is critically dependent on CD4 TFH cells.

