### 11.2 Sample Size Considerations

In our preliminary studies, we found that vaccine-elicited plasmablasts that are specific to the stalk region of HA (the broadly protective region) were induced in 20% of subjects after receiving the annual inactivated trivalent influenza vaccine. This analysis was done on only 20 subjects and we would like to test the consistency of our observation with a larger sample size of 50.

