### 11.4 Final Analysis Plan

We will be utilizing the paired Student's *t*-test to determine whether the observed increase in serum antibody titers from baseline to 4 weeks after vaccination is significant or not. We do not anticipate any major change in our analysis strategy. For all of this analysis we will work the Emory/UGA CEIRS Data Management Team headed by [name] using the approved Data Management Plan for this contract.

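### As printed, the primary seroconversion rule places a baseline HI titer of exactly 1:10 in neither clause, so for that strain no rise can count as seroconversion

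*Combined protocol and SAP*

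**What the plan says.** Section 3.2.1 lists one primary outcome measure, the percentage of subjects who seroconvert between Day 0 and Day 28. The rule has two alternatives: "pre-vaccination HI titer < 1:10 and a post-vaccination HI titer > 1:40 or a pre-vaccination HI titer > 1:10 and a minimum" four-fold rise in the post-vaccination titer. This is the only definition of seroconversion in the document.

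The other places that touch on it add nothing about boundary values:

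- Section 8.2, under the research assays, states what will be measured: "We will measure the HAI titers, neutralizing antibody responses, and the influenza-specific serum antibody levels". It gives no dilution series, no lowest dilution and no value for titers below detection.
- Section 11.4 plans a paired t-test to "determine whether the observed increase in serum antibody titers from baseline to 4 weeks after vaccination is significant or not". It does not restate or analyse the seroconversion percentage.
- Section 11.2 bases the sample size on "vaccine-elicited plasmablasts that are specific to the stalk region of HA", not on seroconversion.
- Section 4 sets the size: "The enrollment goal is up to a total of 70 subjects".

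**The concern.** The two clauses read as complementary groups, low baseline and detectable baseline, but the dividing value belongs to neither. Someone who programs the rule as printed scores every subject at exactly 1:10 as a non-responder, however large the rise. Someone who notices the gap has to make a choice that the plan does not document, possibly with the titers already in hand.

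The outcome is a percentage of subjects, so those affected stay in the denominator and can only drop out of the numerator. Any error therefore runs in one direction, towards a lower rate.

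Baselines at the low end of the detectable range are plausible in this population. Sections 5.1 and 5.2 exclude only vaccination or infection in the current season. Section 5 says: "Individuals who complete the study will be given the option to re-enroll in subsequent years". Section 2.1 notes that "re-vaccination is still recommended because antibody levels decline over the course of a year". None of this says how many subjects start at exactly 1:10.

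**Working it through.** **Inputs.** The rule comes from Section 3.2.1. The enrollment ceiling comes from Sections 4 and 5: "The study will enroll 10 healthy volunteers per vaccination season in years 1, 2, and 4", and at most 20 in each of years 5 and 6, so 3 × 10 + 2 × 20 = 70. The plan states no expected seroconversion rate, so there is no figure of its own to reproduce.

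**Step 1: the rule as printed.** Let a be the Day 0 titer and b the Day 28 titer, both as reciprocals. Seroconversion = (a < 10 and b > 40) or (a > 10 and b/a ≥ 4). At a = 10 both baseline conditions are false, so the result is false for every b.

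- a = 10, b = 640: b/a = 64, not counted.
- a = 20, b = 80: b/a = 4, counted.

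**Step 2: which titer patterns change.** The dilution series is not given, so two are assumed.

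Assumed two-fold series <10, 10, 20, …, 1280 (9 levels, 81 pairs). Qualifying pairs by baseline <10, 10, 20, 40, 80, 160, 320:

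- Literal rule: 5 + 0 + 5 + 4 + 3 + 2 + 1 = 20.
- Second clause inclusive at 1:10: 5 + 6 + 5 + 4 + 3 + 2 + 1 = 26. The six added pairs are 10 to 40, 80, 160, 320, 640 and 1280.
- Post-vaccination threshold also inclusive at 1:40: 6 + 6 + 5 + 4 + 3 + 2 + 1 = 27. The one further pair is <10 to 40.

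Assumed two-fold series <8, 8, 16, …, 2048 (10 levels, 100 pairs). No titer equals 10 or 40, so the rules agree: by baseline <8, 8, 16, 32, 64, 128, 256, 512, each gives 6 + 6 + 6 + 5 + 4 + 3 + 2 + 1 = 33.

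In neither series does a pair count under the literal rule but fail the inclusive one, which confirms the direction of the error.

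**Step 3: effect on the rate.** Let k be the number of subjects with a = 10 and b ≥ 40. Then inclusive rate − literal rate = k/N. With k = 1 and N = 70, 1/70 = 1.43 percentage points. The documents do not allow k to be estimated; on the second assumed series k = 0.

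**The case against.** **The strict signs may not be in the original.** Both greater-than signs in the rule stand where an inclusive sign would be expected, and an underlined greater-than sign can lose its underline when a PDF is converted to text. Inclusive signs do survive in Sections 5.1, 5.2 and 8.2, which shows that they can come through but does not prove what was printed in Section 3.2.1. This stands as a reason to look at the source file first.

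**The intent is easy to guess.** An analyst would probably query the gap or read the second clause inclusively. That is fair, but a rule for the primary outcome should not depend on a guess, and no other section confirms it.

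**The consequence is limited.** The study is single-arm, the stated primary objective concerns plasmablasts and memory B cells, and Section 11 neither tests the percentage nor sizes the study on it. This stands, and it bounds how serious the point can be.

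**The 1:40 threshold is a different matter.** A reader might infer that the strict sign at 1:40 is a second gap, because a rise from below 1:10 to exactly 1:40 exceeds four-fold and is still rejected. It is not a gap. Requiring a titer above 1:40 from a low baseline is a coherent, stricter cut-off, and every case is still classified.

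**Conclusion.** The point holds on the printed text, conditional on the symbols being strict in the source. For any strain scored, a baseline of exactly 1:10 is unclassified and cannot count. The understatement is 1/N per affected subject with at least a four-fold rise, or 1.4 points at 70 enrollments. The number of such subjects is unknown and may be zero.

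The documents do not support four stronger readings that a reader might draw:

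- **That about a quarter of responses are lost** (20 against 27). Those are counts of possible titer patterns on an assumed series, not of subjects, and one of the seven concerns 1:40 rather than 1:10.
- **That a seasonal rate could shift by 5 or 10 points per subject** (1/20 or 1/10). The plan does not say that seroconversion will be reported by season.
- **That the subject is excluded altogether.** Section 3.2.1 names no strain, and Section 2.1 describes vaccines with three or four. If a response to any strain sufficed, a subject at 1:10 for one strain could still count through another.
- **That the study's inference or size is compromised.** The paired t-test uses titers, and the sample size rests on stalk-specific plasmablasts.

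It is still worth correcting, because it concerns the written definition of the only primary outcome measure.

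**What to change.** 1. Check the comparison signs of Section 3.2.1 in the source file. If the baseline sign in the second clause is already inclusive, nothing needs to change on this point.
2. If it is strict, restate the second clause as a baseline titer ≥ 1:10 with at least a four-fold rise at Day 28. Every baseline then falls in exactly one clause.
3. In the same check, confirm whether the post-vaccination threshold in the first clause was meant as > 1:40 or ≥ 1:40, and print the one intended.

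The cost is one symbol, or two if the 1:40 sign also changes. No new data are needed, because the Day 0 and Day 28 titers are collected in any case. Enrollment has already begun, so the correction should be recorded as a dated clarification, preferably before the percentage is calculated.

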##### 3.2.2 Secondary Outcome Measures

Investigation of the longevity of humoral immunity to influenza virus in humans will be performed by:

- Measuring influenza hemagglutinin stem-specific and head-specific memory B-cells and serum antibody levels at days 0, 28, and 180.
- For serum antibody responses directed against the HA head or stem regions, we will determine the endpoint IgG titers at days 0, 28 and 180 after vaccination.  
For memory B cells, we will determine the frequency of HA head- or stem-specific IgG-secreting memory B cells per total IgG-secreting cells at days 0, 28 and 180 after vaccination.
- Plasmablast responses against either the HA head or stem antigens will be determined by direct ex vivo ELISPOT at day 7 after vaccination.
- Expression of human influenza-specific monoclonal antibodies from Day 7 plasmablasts and assessing their functional by ELISA, HAI, and virus neutralization assays.

### 3.2.3 Exploratory Outcome Measures

Characterization of HA-specific plasmablasts and memory B cells after influenza vaccination will be performed using samples from the following timepoints:

- Sequencing of antibodies from single cell sorted plasmablasts and deep immunoglobulin sequencing of RNA from bulk sorted plasmablasts and plasma cells will be carried out using day 7 samples, and the following assays will be performed:
  - Cloning of human influenza-specific monoclonal antibodies and analysis of strain specificity by ELISA, HAI, and virus neutralization assays.
  - Sequence analysis of influenza-specific antibodies to characterize patterns in VDJ usage, CDR3 region length, and numbers of replacement vs. silent mutations.
- Protein sequencing of serum antibodies which bind to vaccine antigens at different timepoints (day 0, 28, 180) post vaccination.
- Define the gene expression profile of HA-specific plasmablasts and memory B cells (day 7)
- Examine the clonal diversity of HA-specific plasmablasts and memory B cells (day 7)

Investigation of the longevity of humoral immunity to influenza virus in humans will be performed by:

- Identifying which plasmablast clones persist to late time points and examine whether the same plasmablast clones are re-amplified after vaccination.
- Examining associations between specific antibody features (hypermutation level, antigen binding affinity, cross reactivity to previous vaccine strains) and the likelihood of long-term persistence in each compartment.

Using proteomics directed cloning to identify the dominant B-cell clones producing influenza-specific and hemagglutinin stalk-specific antibodies in the serum of vaccine recipients and infected subjects.

#### 4 STUDY DESIGN

Longitudinal assessment of the study participants will be made at every study visit. Assessments will be performed at day 0, 7, 14, 28, 90 and 180 days after immunization as outlined in the Schedule of Events (appendix A). Participants will be monitored by the study nurse for the presence of both expected reactions to vaccination and for unexpected adverse reactions for 15 minutes following vaccination. Subject enrollment will be contingent upon the availability of the seasonal flu vaccine and will end upon expiration of the product.

Due to the COVID-19 pandemic, all non-essential research was halted in mid-March 2020. New enrollments were placed on hold for this study. Follow-up visits were also halted, which impacted the timing of participants' subsequent follow-up visits. For this study, there are participants whose Day 180 visits were impacted. We will request an expansion of the study window for the participants whose Day 180 visits were impacted. Additional details regarding this are detailed further in the protocol. None of the other visits were impacted.

The clinical study is designed to characterize the specific immunologic response to influenza vaccination of humans using commercially available influenza vaccine. This study will compare and contrast the response of individual components of the immune system using licensed seasonal inactivated influenza vaccine. This vaccine is FDA approved for protection against influenza infection but may have different effects on different components of the immune system. The enrollment goal is up to a total of 70 subjects. The subjects will have blood drawn at designated time points to have ex-vivo analysis of specific immunologic responses measured. Blood will be drawn at screening, day 0, 7, 14, 28, 90 and 180 study visits.

Due to the COVID-19 pandemic, there are participants whose Day 180 visits were impacted. We are requesting that the window for the day Day 180 visit be expanded by 90 days. Day 180 is the final visit/study endpoint for this study.

## 5 STUDY POPULATION

The study will enroll 10 healthy volunteers per vaccination season in years 1, 2, and 4, to analyze the immune response to influenza vaccination in healthy individuals. For years 5 and 6, we anticipate enrolling a maximum of 20 participants, to analyze the immune response to influenza vaccination in healthy individuals.

Total enrollment goal is up to a total of 70 subjects. Individuals who complete the study will be given the option to re-enroll in subsequent years as long as they continue to meet all inclusion/exclusion criteria. Re-enrolling subjects will be re-consented, given new subject identifiers, and counted towards the enrollment number goal for each year of participation.

- Males and non-pregnant females confirmed to be non-pregnant immediately prior to vaccination, aged 18 - 49, inclusive.
- Study subjects will be drawn from existing populations of students, staff, faculty, or volunteers at Emory University or other eligible healthy adults who may hear of the study by word of mouth.
- Study subjects will be recruited via word of mouth and placement of recruitment flyers in key locations on campus. Social media messaging via Facebook and Twitter will also be used in an effort to increase the number of enrollees into this study.

### 5.1 Inclusion Criteria

For inclusion into the study, a subject must satisfy all of the following criteria:

1. Male or female subjects between 18 and 49 years of age, inclusive
2. Subjects capable of providing written informed consent prior to initiation of any study procedures. Subjects able to understand and comply with planned study procedures and be available for all study visits
3. Screening labs within normal limits per the local laboratory normal ranges or considered to be not clinically significant by the investigator. Normal laboratory ranges are as listed below:
  - A. Hematology:
    - Hemoglobin: Male- 12.9-16.1 gm/dL, Female- 11.4-14.4 gm/dL
    - White blood cells (WBC): Male- 4.2-9.2/uL, Female- 4-10/uL
    - Platelet count: 150-400/uL
  - B. Chemistries:
    - Kidney function:Glomerular filtration rate (GFR) >/= 60 mL/min/1.73 m^2;

- Liver enzymes: Albumin  $\geq 3.5$  g/dL; ALT  $<66$  U/L; AST  $<62$  U/L
- 4. Subjects who have not received the seasonal influenza vaccine in the current flu season and are not suspected to have had an influenza infection in the current flu season.
- 5. Female subjects of child bearing potential must have a negative urine pregnancy test at the screening visit, enrollment visit and all subsequent study visits longer than 14 days since the last pregnancy test.

